Keywords: Pulmonary Arterial Hypertension; PAH; Imatinib; TKI

STUDY SUMMARY

TITLE:	Positioning Imatinib for patients with Pulmonary Arterial Hypertension (PIPAH Study)									
PHASE:	II	II								
INVESTIGATIONAL MEDICINAL PRODUCT:	Imatinib	Imatinib mesilate								
DESIGN:	Open-lab	Open-label, multi-centre comprising two parts - see Appendix 1								
	Part 1 uses the Bayesian continual reassessment method to define the highest tolerated dose.									
		kes this dose forward into an endpoptimal two-stage design.	point efficacy study using a							
OBJECTIVE(S):	Part 1: To identify the highest tolerated dose of Imatinib (between 100mg and 400mg once daily for 4 weeks) in patients with Pulmonary Arterial Hypertension (PAH). Part 2: To assess the efficacy of Imatinib administered at the highest tolerated dose (once daily for 24 weeks) on pulmonary vascular resistance (PVR) in PAH patients according to genes that influence the									
	actions o	f PDGF (platelet derived growth fac	ctor).							
INTERVENTION:	Imatinib - oral administration once daily for up to 24 weeks									
PRIMARY OUTCOME MEASURES:	Part 1: Discontinuation of the drug for more than 5 consecutive days due to Grade 2 or above Adverse Events defined by the National Cancer Institute (NCI) Common Terminology Criteria for Adverse Events (version 5.0, 2017), adapted for this study - see Appendix 2 Part 2: The primary efficacy endpoint is a binary variable. For patients with a baseline PVR >1000 dynes·s·cm ⁻⁵ , success is defined by an absolute reduction in PVR of ≥300 dynes·s·cm ⁻⁵ at 24 weeks. For patients with a baseline PVR ≤1000 dynes·s·cm ⁻⁵ , success is a 30% reduction in PVR at 24 weeks.									
POPULATION:	Up to 43	individuals with PAH. Recruitment	is competitive among sites.							
STUDY CENTRES:	Site ID	Site Name	Academic Affiliation							
	4410	Hammersmith Hospital	Imperial College London							
	4420	Royal Papworth Hospital	University of Cambridge							
	4430	Royal Hallamshire Hospital	University of Sheffield							
	4440	Royal Free Hospital	University College London							
	4450 Royal Brompton Hospital Imperial College Lon 4460 Golden Jubilee National Hospital University of Glasgo									
	4470	Newcastle Freeman Hospital	Newcastle University							
	4480 Royal United Hospital University of Bath									
STUDY DURATION:	Up to 48 months First Patient First Visit: Q1, 2021 Last Patient Last Visit: Q2, 2024									

ELIGIBILITY

Inclusion criteria:

- 1. Subjects aged between 18-80 years old
- **2.** PAH which is idiopathic; PAH heritable; PAH associated with connective tissue disease; PAH after ≥ 1 year repair of congenital systemic to pulmonary shunt, or PAH associated with anorexigens or other drugs
- **3.** Subjects willing to be genotyped for genes that influence PDGF activity
- 4. Resting mean pulmonary artery pressure ≥25 mmHg, pulmonary capillary wedge pressure ≤15 mmHg, PVR >5 wood units, and normal or reduced cardiac output, as measured by right heart catheterisation (RHC) at entry
- **5.** Six-minute walking distance >50m at entry
- **6.** Stable on an unchanged PAH therapeutic regime comprising at least 2 therapies licensed for PAH (any combination of endothelin receptor antagonist, phosphodiesterase inhibitor or prostacyclin analogue) for at least 1 month prior to screening
- **7.** Able to provide written informed consent prior to any study mandated procedures
- 8. Contraception: Fertile females (women of childbearing potential) are eligible to participate after a negative highly sensitive pregnancy test, if they are taking a highly effective method of contraception during treatment and until the end of relevant systemic exposure. Fertile males who make use of condom and contraception methods during treatment and until the end of relevant systemic exposure in women of childbearing potential -see details in section 4.3.1-

Exclusion criteria:

- 1. Unable to provide informed consent and/or are non-fluent speakers of the English language
- 2. Hypersensitivity to Imatinib or to any of the excipients
- **3.** Clinically-significant renal disease (confirmed by creatinine clearance <30 ml/min per 1.73m²)
- **4.** Clinically-significant liver disease (confirmed by serum transaminases >3 times than upper normal limit)
- 5. Patients receiving oral and/or parenteral anticoagulants*
- **6.** Anaemia confirmed by haemoglobin concentration <10 g/dl
- 7. History of thrombocytopenia
- **8.** Individuals known to have haemoglobinopathy sickle cell disease, thalassaemia
- **9.** Hospital admission related to PAH or change in PAH therapy within 3 months prior to screening
- **10.** History of left-sided heart disease and/or clinically significant cardiac disease, including but not limited to any of the following:
 - a. Aortic or mitral valve disease (stenosis or regurgitation)

- defined as greater than mild aortic insufficiency, mild aortic stenosis, mild mitral stenosis, moderate mitral regurgitation
- b. Mechanical or bioprosthetic cardiac valve
- c. Pericardial constriction, effusion with tamponade physiology, or abnormal left atrial size.
- d. Restrictive or congestive cardiomyopathy
- e. Left ventricular ejection fraction ≤50% (measured in echocardiogram at screening)
- f. Symptomatic coronary disease
- g. Significant (2+ for regurgitation) valvular disease other than tricuspid or pulmonary regurgitation
- h. Acutely decompensated left heart failure within 1 month of screening
- i. History of untreated obstructive sleep apnoea
- 11. Evidence of significant lung disease on high-resolution CT (if available) or recent (performed within 12 months) lung function, where FEV1 < 50% predicted and FVC < 70% predicted, and DLCO (or TLCO) < 50% predicted if any CT abnormalities; judged by the Site Physician

- **12.** Patients with a history of uncontrolled systemic hypertension
- 13. Acute infection (including eye, dental, and skin infections)
- 14. Chronic inflammatory disease including HIV, and Hepatitis B
- **15.** Women of childbearing potential who are pregnant or breastfeeding (if applicable)
- 16. Previous intracerebral haemorrhage
- **17.** Patients who have received an Investigational Medicinal Product (IMP) within 5 half-lives of the last dose of the IMP or 1 month (which ever is greater) before the baseline visit
- *this does not apply to single antiplatelet therapy

TREATMENT:

There are two parts to the study. Part 1 will recruit 6 to 13 patients. The objective is to identify the highest tolerated dose. Part 2 will follow on. It will recruit a separate group of patients, up to 34, to evaluate the efficacy of the highest tolerated dose.

Patients will be invited to participate by one of the 8 NHS partner sites specialised in the management of PAH. Suitable patients will be treated with Imatinib once daily for up to 24 weeks. Patients will be asked to keep diaries for as long as they will be taking the study drug to ensure compliance.

Part 1: Some patients will have an insertable FDA/CE cardiac rhythm monitor and pulmonary artery pressure monitor that captures cardiopulmonary haemodynamics and daily activity. These patients will be provided with a remote monitoring system to capture daily blood pressure, oxygen saturations and body weight. This permits remote monitoring with the option to attend the hospital, as required. The patients without a monitor will attend their specialist hospital site for a baseline assessment (inclusive of a right heart catheterisation, RHC),

and then again at the end of Week 4 to assess tolerability, with telephone assessments at the end of Weeks 1, 2 and 3.

The first patient will receive Imatinib 100mg (x1) once daily. Subsequent patients will enter the trial at no less than 4 week intervals and receive a dose of Imatinib (up to 400mg) based on the experience of the previous patient(s) at 4 weeks, using a statistical model to identify the most likely highest tolerated dose. By definition, the highest tolerated dose is reached in this trial when there is a 20% probability that a patient will not be able to continue the drug for 5 consecutive days.

All patients who are tolerating Imatinib will be asked to continue on their assigned dose to the end of week 24 and their clinical response will be measured by the change in PVR (measured using the implanted monitor or, where a patient does not have a monitor by RHC).

Part 2: All patients will receive the highest tolerated dose (defined in Part 1) for 24 weeks. Patients will be recruited as suitable (i.e. there is no staggering) and monitored for safety at the end of Weeks 4, 8, 12 and 24, with telephone assessments at the end of Weeks 16, 20 and 28. Clinical response will be measured by change in PVR from baseline at Week 24. The primary efficacy endpoint is a binary variable: for patients with a baseline PVR >1000 dynes·s·cm⁻⁵, success is defined by an absolute reduction in PVR of ≥300 dynes·s·cm⁻⁵ at 24 weeks; for patients with a baseline PVR ≤1000 dynes·s·cm⁻⁵, success is a 30% reduction in PVR at 24 weeks.

An interim analysis is planned after 13 patients have completed the 24-week treatment on the highest tolerated dose; some patients from Part 1 will be evaluable if they have completed 24 weeks on the highest tolerated dose. If there are 1 or no responses in these patients, the study will be stopped. Otherwise, additional patients will be recruited for a total of 34 evaluable patients (target for Part 2). The null hypothesis will be rejected if 7 or more responses are observed in the 34 patient cohort.

Blood levels of Imatinib will be measured in each patient at baseline and at the end of Weeks 4 and 24. A trough level (noting the time for last dose) will be measured at Week 4 and Week 24.

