4. INVESTIGATIONAL PLAN

4.1 Overall study design and plan

Patients will be invited to participate by their local designated pulmonary hypertension hospital. Suitable patients will be treated with Imatinib once daily for up to 24 weeks. The study is in two parts. The screening and consenting procedures are the same for Parts 1 and 2.

Part 1 will recruit 6 to 13 patients to identify the highest tolerated dose of Imatinib within the 100mg to 400mg per day range. This dose will then be used in Part 2 in a separate group of patients to assess efficacy according to the genes that relate to PDGF activity. It is necessary to find a single dose to maximise the opportunity to assess variation in response by genotype (i.e. reduce the influence of variation in exposure). It is necessary to find the highest tolerated dose to maximise the opportunity to capture a clinical response (i.e. reduce the chance of missing an effect). A starting dose of 100mg is based on experience from compassionate use; some patients, such as the case report above, have reported benefit from this dose. Doses of 200mg to 400mg daily were investigated in IMPRES (10) and many patients ended up on 200mg daily in the extension study. Our prior model of toxicity -see Section 10; skeleton- predicts that 200mg daily is likely to be the highest tolerated dose in PAH, and Part 1 is designed to explore this. A lower dose will be investigated in the efficacy phase if better tolerated.

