4.3.5 Subject identification and replacement policy

After informed consent is obtained, patients who are screened will be assigned a 7-digit permanent identification number (subject ID) such that all patients from each research site are given consecutive identification numbers in successive order of inclusion. The first 4 digits of the will be the designated research site ID, and the last 3 digits will be assigned at the research study centre (e.g., if the site ID is 4410, the third patient screened at 4410 site, would be given the number of 4410003).

A patient who is screened but fails to proceed into baseline assessment (e.g., because entry criteria were not met or enrolment did not occur within the specified time frame) may be considered for screening again. Rescreening will be permitted by the site Investigator on a case-by-case basis. A new informed consent form will be signed in any case of re-screening. A new subject ID will be assigned to the subject. Patients who are discontinued will be replaced. Each replacement is by a default a new subject, who will be assigned a completely new subject ID.

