10. STATISTICS AND DATA ANALYSIS

Part 1 - Dose finding phase

The highest tolerated dose of Imatinib will be determined using a Bayesian continual reassessment method. An initial dose/toxicity skeleton was generated based on a one-parameter power model and a prior guess of toxicities based on expert opinion and data from the IMPRES trial (10) - see Figure 6. Patients will be recruited into the trial individually; the first patient will receive the lowest dose of Imatinib (100mg daily). The highest tolerated dose will be reassessed after each patient completes follow-up and recommended as the dose for the subsequent patient. Dose escalation between patients will be conducted in increments, with no patient receiving more than 100mg than the previous patient (within the 100mg-400mg dose range), guided by the previous dose administered using a statistical model and with oversight from an Independent Data Monitoring Committee. A safety stopping rule has also been imposed if the model identifies with 90% certainty that the lowest dose has a higher toxicity than the target toxicity level (TTL) of 20%. The minimum and maximum number of patients to enter Part 1 of the trial will be 6 and 13, respectively. Under these constraints, using simulation studies we have explored the operating characteristics of this trial design. If our prior toxicities hold true -see Figure 6- the trial design will correctly predict a dose within 10% of the TTL 90% of the time. After the 13th patient completes follow-up (or if a stopping rule is triggered or otherwise stopped early as described in section Premature Termination of the Trial) the toxicities and 90% credible intervals will be calculated for each dose level to generate the dose/toxicity quotient based on the data and prior experience from compassionate use. The highest tolerated dose will be recommended as the dose closest to 20% toxicity. We will also report SAE counts and toxicity incidence with or without withdrawal from study.

Extension phase

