The objective of Part 1 is to recommend a dose of imatinib for Part 2. While this is based on tolerability at 4 weeks, the inclusion of some patients with implanted CardioMEMSTM Heart Failure system and Fitbit activity monitor devices provides the opportunity to record the effect of imatinib on the pulmonary circulation and exercise capacity. These data can inform a harm-benefit assessment around the highest tolerated dose. To investigate this, 4 additional patients (patients 14 to 17) with an implanted CardioMEMSTM Heart Failure system and a Fitbit activity monitor will be recruited and treated with a dose of imatinib at or below the highest

PIPAH Study Page 38 of 47

tolerated dose suggested by the statistical model from Part 1 to gather further data to inform potential benefit. This approach is in line with recommendations from the independent Trial Steering and Data Monitoring (and Ethics) Committees who continue to provide oversight. Sequential recruitment is not required and enrolment of two or more patients in parallel is permitted in the extension phase.

Part 2 - Efficacy Phase

Treatment efficacy at the pre-determined highest tolerated dose will be assessed using a Simons two stage design. A null hypothesis that the true response rate is 0.10 will be tested against a one-sided alternative. The first stage interim analysis will happen after 13 patients have completed the 24-week treatment. If there are 1 or no responses# the study will be stopped. If there are 2 or more responses the trial will continue and recruit another 21 patients, creating a maximum sample size of 34 patients. After the final patient is recruited the null hypothesis will be rejected if 7 or more responses are observed. This design ensures a type I error rate of 0.042 and a power of 0.8034 when the true response rate is 0.27. The expected sample size under the null hypothesis is 21 and the probability of an early termination is 0.6213.

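### The stated maximum of 43 participants does not follow from the protocol's own numbers, which allow up to 51 before overlap and replacements

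*Protocol*

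**What the plan says.** - **Total.** The Population row of the Study Summary reads "Up to 43 individuals with PAH". The protocol shows no derivation of this figure, and section 4.1 gives no overall total.
- **Part 1.** The Study Summary and section 4.1 both say "Part 1 will recruit 6 to 13 patients". Section 10 agrees: "The minimum and maximum number of patients to enter Part 1 of the trial will be 6 and 13, respectively".
- **Extension phase.** Section 10 then adds "4 additional patients (patients 14 to 17" in the numbering), treated at or below the highest tolerated dose that the model suggests. The Study Summary and section 4.1 do not mention them.
- **Part 2.** The Treatment part of the Study Summary says of Part 2: "It will recruit a separate group of patients, up to 34, to evaluate the efficacy of the highest tolerated dose". Section 4.1 also calls the group separate: "This dose will then be used in Part 2 in a separate group of patients to assess efficacy".
- **Carry-over.** The Study Summary text on the interim analysis says that "some patients from Part 1 will be evaluable if they have completed 24 weeks on the highest tolerated dose". Section 4.1 repeats the idea and has recruitment run until 34 patients in all are evaluable. Neither place says how many are expected to carry over.
- **Replacement.** Section 4.3.5: "Patients who are discontinued will be replaced". Each replacement is a new subject, and no limit is set.

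**The concern.** A figure given as an upper limit should hold whatever happens within the plan. Here the parts add up to more than the stated limit, and the extension phase widened the gap. Appendix 3 lists section 10 as the only section given new substantive text in Amendment 04, and the Study Summary total still reads 43.

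Two things are at stake. If 43 is not treated as binding, the trial can pass its own declared maximum while doing exactly what the protocol tells it to do. If 43 is treated as binding, Part 2 may run out of places before it has the 34 evaluable patients on which its decision rule rests. The protocol does not say which applies.

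**Working it through.** **Inputs**

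- Part 1 maximum: 13 (Study Summary; sections 4.1 and 10)
- Extension: 4 (section 10)
- Part 2: up to 34 (Study Summary; section 10)
- Simon design: first stage 13, stop at 1 or fewer responses; total 34, reject at 7 or more; null rate 0.10, alternative 0.27 (section 10)
- k: number of patients from Part 1 or the extension who count among the 34 (allowed, not stated)

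**Step 1: is 34 right?** Let X1 be the first-stage responses in 13 patients and X2 the second-stage responses in 21. The probability of rejecting at response rate p is the sum over x = 2 to 13 of P(X1 = x) × P(X2 ≥ 7 − x). The exact binomial calculation gives:

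| Quantity | Stated | Recomputed |
|---|---|---|
| Type I error (p = 0.10) | 0.042 | 0.0420 |
| Power (p = 0.27) | 0.8034 | 0.8034 |
| Probability of early termination under the null | 0.6213 | 0.6213 |
| Expected sample size under the null | 21 | 13 + (1 − 0.6213) × 21 = 20.95 |

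The 34 stands.

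**Step 2: does 43 follow as a maximum?**

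- Without the extension, no overlap: 13 + 34 = 47, which is 47/43 = 1.09 times the stated total.
- With the extension, no overlap: 13 + 4 + 34 = 51, which is 51/43 = 1.19 times the stated total.

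Replacements under section 4.3.5 would come on top of either figure.

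**Step 3: what would make it 43?** With overlap the totals are 47 − k and 51 − k.

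- 47 − k = 43 gives k = 4 of 13.
- 51 − k = 43 gives k = 8 of 17.
- 9 + 34 = 43 also works arithmetically, but 9 is not the Part 1 maximum.

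If 4 carried over with the extension in place, the total would be 51 − 4 = 47.

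**Step 4: what if 43 were enforced as a cap?** After 17 patients in Part 1 and the extension, 43 − 17 = 26 places remain, so 26 + k patients can be evaluable, assuming every Part 2 patient is evaluable. Keeping the 13-patient first stage and the threshold of 7 responses, the formula in Step 1 with the smaller second stage gives:

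| k carried over | Evaluable | Type I error | Power at 0.27 |
|---|---|---|---|
| 0 | 26 | 0.012 | 0.57 |
| 4 | 30 | 0.024 | 0.71 |
| 8 | 34 | 0.042 | 0.80 |

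The loss is in power, not in type I error, and it vanishes at k = 8.

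**The case against.** The strongest reply is that the protocol counts evaluable patients, not new enrolments. The Study Summary and section 4.1 let eligible Part 1 patients count towards the 34, and wording of the form up to 34 leaves room for fewer new recruits. On that reading 47 and 51 are ceilings with no overlap, not the totals that the design must reach, and 43 is attainable. This stands, and the point is worded accordingly.

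It does not rescue 43 as a maximum. Carry-over depends on how many Part 1 patients happen to receive the dose finally chosen and then stay on it for 24 weeks. Extension patients may be treated below that dose, so they need not contribute. An upper limit has to cover the case k = 0. The carry-over text also sits badly beside the two statements that Part 2 is a separate group.

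Three stronger readings are tempting, and the documents do not support them.

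- **The 7-of-34 rule and its error rates no longer apply.** A reader might infer this from the 26 remaining places. It follows only if 43 is enforced and fewer than 8 of 17 carry over. The 43 appears once, in a summary row, and section 11.6 does not list it among the conditions for ending recruitment.
- **A specific larger total once replacements are included.** A reader might apply the protocol's 20% as a drop-out rate. That 20% is the target toxicity level for dose finding at 4 weeks, not loss over 24 weeks in Part 2. The protocol gives no figure for the latter.
- **Replacement should be dropped in Part 2 so that 51 is firm.** This would reverse section 4.3.5. It is a design change, not a correction of the head count.

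**Conclusion.** The point holds as an inconsistency in the stated enrolment. The figure of 43 is not the maximum that the current protocol gives. That maximum is 47 without the extension and 51 with it, less any overlap k and before replacements. Reaching 43 needs k = 4 of 13, or k = 8 of 17 with the extension, and no section states or guarantees either.

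The efficacy design is sound: 34 evaluable patients, type I error 0.042 and power 0.8034 all reproduce, and they do not depend on the total head count. The only statistical risk is conditional. If 43 were enforced and nobody carried over, power at a response rate of 0.27 would be about 0.57. That figure assumes 17 patients in Part 1 and the extension, 26 evaluable in Part 2 and an unchanged threshold of 7. The matter should be corrected, but it is not a flaw in the test.

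**What to change.** Amend the text so that one maximum follows from its parts:

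1. In the Population row of the Study Summary, state 51 (13 + 4 + 34, no overlap), or 51 minus an assumed overlap that is given as a number.
2. Say whether replacements under section 4.3.5 are included in that figure or come on top of it.
3. In the Study Summary and section 4.1, add the 4 extension patients to the Part 1 size of 6 to 13.
4. Reconcile the descriptions of Part 2 as a separate group (Study Summary, section 4.1) with the text in the same two places that lets Part 1 patients count among the 34 evaluable.

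The Simon sample size, decision rule and error rates need no change. The cost is a wording amendment, and the declared total becomes larger unless an overlap of 8 can be justified.
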